## 1. INTRODUCTION

This statistical analysis plan (SAP) describes the statistical analysis methods and data presentations to be used in tables, figures, and listings (TFLs) in the clinical study report (CSR) for Study GS-US-312-1579. This SAP is based on the study protocol amendment 4 dated 15 June 2017 and the electronic case report form (eCRF). The SAP will be finalized before database finalization. Any changes made after the finalization of the SAP will be documented in the CSR.

This study has been terminated. Enrollment to this study was closed on 26 April 2017 based on an updated feasibility assessment in relation to changes in the chronic lymphocytic leukemia (CLL) treatment landscape. Two subjects were enrolled in the Phase 1b portion of the study and no subjects were enrolled in the Phase 2 portion of the study.

### 1.1. Study Objectives

The primary objectives of this study are as follows:

- Phase 1b: To determine the safety and tolerability of the combination of idelalisib with BI 836826 in subjects with relapsed and refractory (R/R) CLL, and to establish the high recommended Phase 2 combination dose (highRP2D) as well as an alternate lower recommended Phase 2 combination dose (lowRP2D) regimen.
- Phase 2: To determine the rates of complete response (CR) and of minimal residual disease (MRD) negativity with the combination at the highRP2D and the lowRP2D.

The secondary objectives of this study are as follows:

- Phase 1b and 2: To evaluate overall response rate (ORR), progression-free survival (PFS), duration of complete response (DCR), duration of response (DOR), and overall survival (OS).
- Phase 2: To further characterize the safety and tolerability of the combination using the highRP2D as well as the lowRP2D regimen.

Due to the early study termination, the study objectives will not be met and the 2 subjects that were enrolled will be assessed for safety only.

### 1.2. Study Design

The Phase 1b portion of the study will evaluate various dose combinations of idelalisib and BI 836826 in sequential cohorts following an initial 7-day idelalisib monotherapy run-in period. The safety data from each cohort will be used as input into the bayesian logistic regression model (BLRM). The output from this model will be used by the safety review team (SRT) to choose the dose combination for evaluation in the subsequent cohort. At completion of Phase 1b, 2 dose

[figure not shown]
combinations will be selected for further evaluation in Phase 2. In the Phase 2 portion of the study, subjects with R/R CLL will be randomly assigned in a 1:1 manner to receive 1 of the 2 dose combinations selected from Phase 1b following an initial 7-day idelalisib monotherapy run-in period.

Approximately 42 evaluable subjects will be enrolled in the Phase 1b portion of the study and 50 evaluable subjects will be randomized in the Phase 2 portion of the study.

Idelalisib tablets will be administered orally twice daily (BID) continuously until disease progression or intolerable toxicity. During the Phase 1b portion of the study, the following dose levels will be tested: 50 mg BID, 100 mg BID, and 150 mg BID; the starting dose level will be 50 mg BID. BI 836826 will be administered as a rate-controlled intravenous (IV) infusion, with a total of 18 doses, from Week 2 through Week 46. During the Phase 1b portion of the study, the starting dose level will be 100 mg, and the highest possible dose tested will be 600 mg.

In both Phase 1b and Phase 2, idelalisib will be administered starting on Week 1, Day 1. Following 7 days of idelalisib, BI 836826 administration will start during Week 2 with an initial dose of 10 mg on Day 8; 50% of the assigned dose will be given on Days 9 and 15, and 100% of the assigned dose will be given on Day 22. Thereafter, 100% of the assigned dose will be administered every 2 weeks through Week 18, and every 4 weeks through Week 46.

Dosing Schema:

The schedule of assessments is in [Appendix 1](#) of this SAP.

Following enrollment of 2 subjects in the Phase 1b portion of the study, the study was terminated and therefore, Phase 2 will not occur. Subjects may remain on study through approximately Week 50 (to include 30-day follow up after last dose of BI 836826). Study procedures have been modified accordingly.

### 1.3. Sample Size and Power

There is no formal hypothesis to be tested in this study; therefore, no formal sample size calculation was performed.

## **2. TYPE OF PLANNED ANALYSIS**

### **2.1. Interim Analyses**

This study does not have a data monitoring committee (DMC). Therefore, no analyses will be conducted for the DMC.

### **2.2. Final Analysis**

After all subjects have completed the study, outstanding data queries have been resolved or adjudicated as unresolvable, and the data have been cleaned and finalized, the final analysis of the data will be performed.

### **2.3. Follow-up Analysis**

Not applicable

### **3. GENERAL CONSIDERATIONS FOR DATA ANALYSES**

By-subject listings will be presented for all subjects in the Safety Analysis Set and sorted by subject identification (ID) number, visit date, and time (if applicable). Data collected on log forms, such as adverse events (AEs), will be presented in chronological order within the subject. The dose cohort to which subjects were initially assigned will be used in the listings. Age, sex at birth, race, and ethnicity will be included in the listings.

Due to the early study termination, planned analyses will not be performed and only safety-related endpoints will be reported for the subjects enrolled in the study.

#### **3.1. Analysis Sets**

Analysis sets define the subjects to be included in an analysis. Analysis sets and their definitions are provided in this section. The analysis set will be identified and included as a subtitle of each table, figure, and listing.

##### **3.1.1. Safety Analysis Set**

The Safety Analysis Set includes all subjects who took at least 1 dose of study drug. This is the primary analysis set for safety analyses.

#### **3.2. Subject Grouping**

Not Applicable

#### **3.3. Strata and Covariates**

This study does not use a stratified randomization schedule when enrolling subjects. No covariates will be included in safety analyses.

#### **3.4. Examination of Subject Subgroups**

There are no prespecified subject subgroupings for safety analyses.

#### **3.5. Multiple Comparisons**

Adjustments for multiplicity will not be made, because no formal statistical testing will be performed in this study.

#### **3.6. Missing Data and Outliers**

##### **3.6.1. Missing Data**

In general, missing data will not be imputed unless methods for handling missing data are specified.

### **3.6.2. Outliers**

All data will be included in the data analysis.

### **3.7. Data Handling Conventions and Transformations**

In general, age (in years) on the first dosing date of study drug will be used for analyses and presentation in listings. For screen failures, the date the informed consent was signed will be used for age calculation. If only the birth year is collected on the eCRF, “01 July” will be used for the unknown birth day and month for the purpose of age calculation. If only birth year and month are collected, “01” will be used for the unknown birth day.

### **3.8. Analysis Visit Windows**

#### **3.8.1. Definition of Study Day**

Study day will be calculated from the first dosing date of study drug and derived as follows:

- For postdose study days: Assessment Date – First Dosing Date + 1
- For days prior to the first dose: Assessment Date – First Dosing Date

Therefore, study day 1 is the day of first dose of study drug administration.

#### **3.8.2. Analysis Visit Windows**

The nominal visit as recorded on the eCRF will be used.

## **4. SUBJECT DISPOSITION**

### **4.1. Subject Enrollment and Disposition**

The following by-subject listings will be provided by subject ID number in ascending order:

- Reasons for premature study drug or study discontinuation
- Reasons for screen failure will be provided by screening ID number in ascending order
- Lot number and kit ID

### **4.2. Extent of Study Drug Exposure and Adherence**

Extent of exposure to study drug will be examined by assessing the total duration of exposure to study drug.

#### **4.2.1. Duration of Exposure to Study Drug**

Total duration of exposure to idelalisib will be defined as last dosing date minus first dosing date plus 1, regardless of any temporary interruptions in idelalisib administration, and will be expressed in days. If the last idelalisib dosing date is missing, the latest date among the study drug end date, clinical visit date, laboratory sample collection date, and vital signs assessment date that occurred during the on-treatment period will be used.

A by-subject listing of study drug administration will be provided for both idelalisib and BI 836826 by subject ID number (in ascending order) and visit (in chronological order).

### **4.3. Protocol Deviations**

Protocol deviations occurring after subjects entered the study are documented during routine monitoring. A by-subject listing will be provided for those subjects with an important protocol deviation.

## 5. BASELINE CHARACTERISTICS

### 5.1. Demographics

A by-subject demographic listing, including age, sex, race, ethnicity, and the informed consent date, will be provided by subject ID number in ascending order.

### 5.2. Other Baseline Characteristics

Other baseline characteristics include body weight (in kg), height (in cm), body mass index (BMI; in kg/m^2), and Eastern Cooperative Oncology Group (ECOG) performance status at screening.

A by-subject listing of other baseline characteristics will be provided by subject ID number in ascending order.

### 5.3. Medical History

General medical history data collected at screening will be listed only. Medical history data will not be coded. A by-subject listing of general and disease-specific medical history will be provided by subject ID number in ascending order.

Time since CLL diagnosis (years) will be calculated by (first dosing date of study drug – date of CLL diagnosis). In deriving the time since CLL diagnosis, all partial dates of diagnosis will be identified, and the partial dates will be imputed as follows:

- If both the day and month are missing but the year is available, then the imputed day and month will be 01 Jan.
- If only the day is missing but the month and year are available, then the imputed day will be the first day of the month.
- If the year is missing, a partial date will not be imputed.

### 5.4. Prior Anticancer Therapy

The regimens and prior therapies that the subjects received and time since the completion of last regimen will be listed based on the Safety Analysis Set. A partial completion date will be imputed using the following algorithm for the last regimen:

- If both the day and month are missing but the year is available, then the imputed day and month will be 01 Jan or the starting date of the last regimen, whichever is later.
- If the day is missing but the month and year are available, then the imputed day will be the first day of the month, or the starting date of the last regimen, whichever is later.
- If the year is missing, no imputation will be done and the completion date will be treated as missing.

Prior radiation therapy and prior surgery/procedure will be listed.

## **6. EFFICACY ANALYSES**

This study was terminated in Phase 1b based on an updated feasibility assessment in relation to changes in the CLL treatment landscape. Since only 2 subjects were enrolled at the time of study termination, efficacy endpoints will not be evaluated and available data will only be listed.

### **6.1. Primary Efficacy Endpoint**

Not applicable

### **6.2. Secondary Efficacy Endpoints**

Not applicable

### **6.3. Exploratory Efficacy Endpoints**

Not applicable

## 7. SAFETY ANALYSES

### 7.1. Adverse Events and Deaths

#### 7.1.1. Adverse Event Dictionary

Clinical and laboratory AEs will be coded using the current version of Medical Dictionary for Regulatory Activities (MedDRA). System organ class (SOC), high-level group term (HLGT), high-level term (HLT), preferred term (PT), and lower-level term (LLT) will be provided in the AE dataset.

#### 7.1.2. Adverse Event Severity

Adverse events are graded by the investigator as Grade 1, 2, 3, 4, or 5 according to Common Toxicity Criteria for Adverse Events (CTCAE) Version 4.03. The severity grade of events for which the investigator did not record severity will be categorized as “missing” for data listings.

#### 7.1.3. Relationship of Adverse Events to Study Drug

Related AEs are those for which the investigator selected “Related” on the AE eCRF to the question of “Related to Study Treatment.” Relatedness will always default to the investigator’s choice, not that of the medical monitor. Events for which the investigator did not record relationship to study drug will be shown as missing in by-subject data listings.

#### 7.1.4. Serious Adverse Events

Serious adverse events (SAEs) will be identified and captured as SAEs if the AEs met the definitions of SAEs that were specified in the study protocol. SAEs captured and stored in the clinical database will be reconciled with the SAE database from the Gilead Drug Safety and Public Health (DSPH) Department before data finalization.

#### 7.1.5. Treatment-Emergent Adverse Events

##### 7.1.5.1. Definition of Treatment-Emergent Adverse Events

Treatment-emergent adverse events (TEAEs) are defined as 1 or both of the following:

- Any AEs with an onset date on or after the study drug start date and no later than 30 days after permanent discontinuation of study drug
- Any AEs leading to premature discontinuation of study drug.

#### 7.1.5.2. Incomplete Dates

If the onset date of the AE is incomplete and the AE stop date is not prior to the first dosing date of study drug, then the month and year (or year alone if month is not recorded) of onset determine whether an AE is treatment emergent. The event is considered treatment emergent if both of the following 2 criteria are met:

- The AE onset is the same as or after the month and year (or year) of the first dosing date of study drug, and
- The AE onset date is the same as or before the month and year (or year) of the date corresponding to 30 days after the date of the last dose of study drug

An AE with completely missing onset and stop dates, or with the onset date missing and a stop date later than the first dosing date of study drug, will be considered to be treatment emergent. In addition, an AE with the onset date missing and incomplete stop date with the same or later month and year (or year alone if month is not recorded) as the first dosing date of study drug will be considered treatment emergent.

If the AE onset date is incomplete and needs to be imputed, the following algorithm will be followed:

- If the day is missing but the month and year are available, then the imputed day will be the first day of the month or the first dosing date if they have the same month and year, whichever is later.
- If the day and month are missing but year is available, then the imputed day and month will be 01Jan or the first dosing date if they have the same year, whichever is later.

#### 7.1.6. Summaries of Adverse Events and Deaths

All AEs and SAEs will be listed based on the Safety Analysis Set.

#### 7.2. Laboratory Evaluations

By-subject listings of laboratory data will be provided by subject ID number and time point in chronological order for hematology, serum chemistry, and urinalysis separately based on the Safety Analysis Set. When values are below the LOQ, they will be listed as such, and hemolized test results will be included. Values falling outside of the relevant reference range and/or having a severity grade of 1 or higher on the CTCAE severity grade will be flagged in the data listings, as appropriate.

A baseline laboratory value will be defined as the last measurement obtained on or prior to the date/time of first dose of study drug.

### **7.2.1. Graded Laboratory Values**

CTCAE Version 4.03 will be used to assign toxicity grades (0 to 4) to laboratory results for analysis. Grade 0 includes all values that do not meet the criteria for an abnormality of at least Grade 1. For laboratory tests with criteria for both increased and decreased levels, analyses for each direction (ie, increased, decreased) will be presented separately.

#### **7.2.1.1. Treatment-Emergent Laboratory Abnormalities**

Treatment-emergent laboratory abnormalities are defined as values that increase at least 1 toxicity grade from baseline at any postbaseline time point, up to and including the date of last dose of study drug plus 30 days for subjects who permanently discontinued study drug. If the relevant baseline laboratory value is missing, any abnormality of at least Grade 1 observed within the time frame specified above will be considered treatment emergent.

### **7.2.2. Liver-related Laboratory Evaluations**

Liver-related abnormalities after initial study drug dosing will be examined using the following laboratory test values for postbaseline measurements:

- AST: > 3 times of the upper limit of reference range (ULN)
- ALT: > 3 x ULN
- Total bilirubin: (a) > 1.5 x ULN; (b) > 2 x ULN
- ALP > 1.5 x ULN
- ALP < 2 x ULN and total bilirubin > 2 x ULN

The listing will include laboratory data from all postbaseline visits up to 30 days after the last dose of study drug. For individual laboratory tests, subjects will be counted once based on the most severe postbaseline values. For the composite endpoint, subjects will be counted once when the criteria are met at the same postbaseline visit date.

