Decrease in leukocytes, neutrophils, thrombocytes, and haemoglobin have frequently been reported in subjects. Drug-related neutropenia was reported in 41% (15/36) of the subjects, with a worst Common Terminology Criteria for Adverse Events (CTCAE) Grade 3 or 4 in 14/36 subjects (32%). Drug-related thrombocytopenia was reported in 31% (11/36), with a worst CTCAE Grade of 3 or 4 in 8 subjects (22%). Corresponding laboratory data showed that neutrophils and thrombocytes declined immediately after the infusion. Anemia was considered drug-related in 28% of the subjects and the highest Grade was CTCAE Grade 3. A drug-related increase of alanine aminotransferase (ALT) was reported in 4 subjects (11%), and an increase of aspartate aminotransferase (AST) was reported in 5 subjects (14%). ALT and AST elevations were Grade 1 and 2 in all subjects except for 1 subject with a Grade 3 ALT elevation. The corresponding laboratory data in these subjects showed short lasting, reversible elevations of AST and/or ALT without concomitant bilirubin elevation. Prior to the next administration of BI 836826, ALT and AST had returned spontaneously to normal or pre-treatment values.

Efficacy was observed at doses ≥ 9 mg. The Overall Response Rate (ORR) was 40% (12/30 subjects); all responses were partial responses. In addition, the decline in absolute lymphocyte count (ALC) was analyzed to assess effect of BI 836826 on CLL tumor load in 25 subjects treated at doses ≥ 9 mg, who had an elevated ALC at baseline and received at least 1 full dose of BI 836826 at the respective dose tier. A decline in ALC by 50% or more as compared to baseline was observed in 80% (20/25 of the subjects) and a reduction to $< 4 \times 10^9/L$ were observed in 56% (14/25) of the subjects.

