- 5) Discontinuation of all cytotoxic chemotherapy and anti-CD20 antibody therapy for ≥ 4 weeks, alemtuzumab for ≥ 8 weeks, targeted therapy for ≥ 2 weeks, and investigational therapy for ≥ 3 weeks before enrollment (Phase 1b) or randomization (Phase 2). For subjects with relapsed CLL most recently treated with BCR pathway inhibitors who, in the opinion of the investigator, will not tolerate waiting 3 weeks, a washout period of > 5 half-lives is allowed. If on a systemic corticosteroid, the dose must be stable for the previous 4 weeks.
- 6) All acute non-hematologic toxic effects of any prior antitumor therapy resolved to Grade ≤ 1 before enrollment with the exception of alopecia or neurotoxicity (Grade 1 or 2 neurotoxicity permitted).
- 7) Eastern Cooperative Oncology Group (ECOG) score of 0, 1, or 2.
- 8) Required baseline laboratory data (within 4 weeks prior to enrollment) as shown in the following table:

Organ System	Parameter	Required Value
Hematopoietic	ANCa	$\geq 1 \times 10^9/L$
	Platelets	$\geq 25 \times 10^9/L$
Hepatic	Serum total bilirubin	$\leq 1.5 \times ULN$ (unless elevated due to Gilbert's syndrome or hemolysis)
	Serum ALT	$\leq 2.5 \times ULN$
	Serum AST	
Renal	CCrb	≥ 30 mL/min
Pregnancy	β -hCGc	Negative
Infection	HIV	Negative HIV antibody
	HBV	Negative HBsAg and negative HBc antibody, or positive HBc antibody and negative for HBV DNA
	HCV	Negative viral RNA (if HCV antibody is positive)
	CMV	Negative viral DNA

- a ANC value to be obtained in the absence of growth factors
 b As calculated by the Cockcroft-Gault formula or measured.
 c For women of child-bearing potential only; serum β -hCG must be negative during Screening and urine pregnancy test must be negative prior to the first dose of study drug
 β -hCG = beta human chorionic gonadotropin, ALT = alanine aminotransferase, AST = aspartate aminotransferase, DNA = deoxyribonucleic acid, eCCr = estimated creatinine clearance, HBc antibody = anti-hepatitis B core antibody, HBsAg = hepatitis B surface antigen, HBV = hepatitis B virus, HCV = hepatitis C virus, HIV = human immunodeficiency virus, Ig = immunoglobulin, PCR = polymerase chain reaction, RNA = ribonucleic acid, ULN = upper limit of normal

- 9) For female subjects of child-bearing potential, willingness to use a protocol-recommended method of contraception from the Screening visit throughout the study, and for 30 days from the last dose of idelalisib or 12 months from the last dose of BI 836826 (whichever is later).

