5.7. Requirements and Recommendations Regarding Specific Adverse Events or Conditions

5.7.1. Transaminase Elevations

Consistent with observations in a dog toxicology study, reversible asymptomatic ALT/AST increases were observed early in the idelalisib program in phase 1 studies (101-02 and 101-07) in subjects with hematologic malignancies. Transaminase elevations generally occurred within 4 to 12 weeks of drug initiation, and resolved spontaneously over a period of 2 to 4 weeks with drug being continued for Grade 1 and 2 elevations and drug withheld for Grade 3 or 4 elevations until resolution. These early observations are consistent with the ongoing experience with idelalisib treatment and transaminase elevations are now well characterized as most frequently asymptomatic, transient and occurring within the first 3 months of treatment.

Grade 1 or 2 elevations commonly resolve despite continued idelalisib treatment and Grade 3 or 4 elevations can be managed by temporarily withholding idelalisib. Successful rechallenge after resolution at either the same or lower dose level of idelalisib has been achieved in the majority of subjects. There has been no evidence of impaired synthetic function. Close monitoring of hepatic laboratory tests during therapy is important to allow for appropriate idelalisib interruption and reinstitution so that subjects may continue with study drug treatment.

Cholangitis manifest as hyperbilirubinemia out of proportion to serum transaminase elevations has been observed. While disease-related factors, neutropenia, toxicity from prior therapies, effects of ongoing supportive care, or pre-existing cholelithiasis may have initiated such events, it is possible that idelalisib played a contributory role. In such subjects, rechallenge with idelalisib has been possible and has not been associated with other severe adverse events.

In selected subjects who experience more complicated hepatic AEs, further workup may be warranted particularly in subjects who first experience a serum ALT/AST elevation ≥12 weeks from the start of study drug therapy, who have an elevation in serum bilirubin concentration or coagulation parameters, or who have other characteristics that suggest an atypical change in transaminase values. Hepatic AEs that require additional workup should be discussed with the Gilead Sciences Medical Monitor.

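### Does the composite liver criterion in SAP 7.2.2 need an AST or ALT condition?

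*SAP*

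**What the plan says.** SAP section 7.2.2 examines postbaseline liver tests against five bullets. Four concern single tests: AST above 3 × ULN, ALT above 3 × ULN, total bilirubin above 1.5 and above 2 × ULN, and ALP above 1.5 × ULN. The fifth pairs two analytes: "ALP < 2 x ULN and total bilirubin > 2 x ULN".

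Two counting rules follow. Single tests use each subject's worst postbaseline value. The pair must be satisfied on one date: "For the composite endpoint, subjects will be counted once when the criteria are met at the same postbaseline visit date". The same section says its listing covers all postbaseline visits up to 30 days after the last dose.

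The reporting context is narrow. SAP section 1 records: "Two subjects were enrolled in the Phase 1b portion of the study". No subject entered Phase 2. SAP sections 3 and 7.7 restrict reporting to listings of safety endpoints. SAP section 7.2 lists serum chemistry by subject in time order and flags values that are outside the reference range or are CTCAE Grade 1 or higher.

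**The concern.** The only date-linked criterion ignores AST and ALT. A subject with bilirubin above 2 × ULN and ALP below 2 × ULN meets it whether the transaminases are normal or very high. Conversely, ALT raised at one visit and bilirubin at another would satisfy the ALT row, the bilirubin row and the composite, although the two were never raised together.

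The protocol gives reasons to care about that concurrence. Section 1.3.3 describes the transaminase findings in the earlier BI 836826 CLL study as "short lasting, reversible elevations of AST and/or ALT without concomitant bilirubin elevation". Section 5.7.1 includes, among the subjects who may need further hepatic workup, those "who have an elevation in serum bilirubin concentration or coagulation parameters". Table 5-3 uses the bilirubin grade within its ALT/AST rows. Inclusion criterion 8 caps bilirubin at 1.5 × ULN, "unless elevated due to Gilbert's syndrome or hemolysis", so a subject could meet the composite because of a pre-existing benign cause.

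If the composite were meant to identify combined transaminase and bilirubin elevation, it would be less specific than intended, and a reader of the report could mistake an isolated bilirubin rise for a combined one.

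**Working it through.** The plan states no figure for this point, so the check is one of logic followed by one of consequence.

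**Inputs.** Thresholds from SAP 7.2.2, all × ULN: AST or ALT > 3 (call this T), bilirubin > 2 (B), ALP < 2 (P). The number of subjects (2) comes from SAP section 1 and the reporting form from SAP sections 3, 7.2 and 7.7.

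**Logic.** T, B and P give 2 × 2 × 2 = 8 possible patterns on a given date.

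| Rule | Definition | Patterns positive |
|---|---|---|
| Bilirubin row above 2 × ULN | B | 4 |
| Composite as written | B and P | 2 |
| Composite with a transaminase term | T and B and P | 1 |

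The three rules are nested: (T and B and P) lies within (B and P), which lies within B. So:

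- patterns the written composite misses relative to the narrower rule: 0;
- patterns it includes in addition: 2 − 1 = 1, namely bilirubin > 2, ALP < 2, AST and ALT both ≤ 3.

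A finer illustrative grid agrees. With AST and ALT each at 1 or 4, and bilirubin and ALP each at 1, 1.8 or 2.5, there are 2 × 2 × 3 × 3 = 36 patterns. The written composite needs bilirubin 2.5 and ALP 1 or 1.8, so it is positive in 4 × 1 × 2 = 8. Requiring AST or ALT above 3 leaves 3 × 1 × 2 = 6. The 2 that drop out have AST and ALT both at 1. These counts describe the rules. They are not rates and do not measure any effect on the trial.

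**Is the additional pattern an error?** That depends on what the composite is for, and the documents do not say. Protocol section 8.8.4 plans CTCAE-grade summaries and shift tables and contains no liver composite. SAP sections 7.2 and 7.2.1 contain none either. The protocol passages that read transaminases with bilirubin are background on another study, triggers for clinical workup, and dose-modification rules. None sets an analysis criterion. Section 5.7.1 also points the other way: "Cholangitis manifest as hyperbilirubinemia out of proportion to serum transaminase elevations has been observed". A bilirubin criterion without a transaminase term would pick up that presentation when ALP is below 2 × ULN; a rule requiring AST or ALT above 3 × ULN could exclude it.

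**Consequence.** AST, ALT, ALP and total bilirubin are all chemistry analytes in protocol Table 6-1, and the study procedures table schedules chemistry as one item per visit. A value above 3 or 2 × ULN lies outside the reference range, so SAP section 7.2 already provides for flagging it. A concurrent rise would therefore appear as flagged values on the same date. For the separated example (visit 1: ALT 6, bilirubin 0.8; visit 2: ALT 0.8, bilirubin 2.4), the listing would show the rises on different dates. With two subjects this can be read directly.

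**The case for a change.** The best case for a change is that a definition should be right however few subjects it covers. Section 7.2.2 still says how subjects are counted, its one composite adds little to the bilirubin row that contains it, and the repair is one line with no new data. All single-test rows would stay, so isolated bilirubin rises would not be hidden. If the SAP is final, a route exists: "Any changes made after the finalization of the SAP will be documented in the CSR".

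The description of the text stands. The composite does not use AST or ALT, and no other section supplies a joint criterion. It is also fair that the sponsor could say in a sentence what the row is for.

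The claim of error does not stand. Calling the row insufficiently specific presupposes a target the documents never set, and they cannot show whether the term was omitted or left out on purpose. The Gilbert's syndrome or hemolysis example is hypothetical, since nothing indicates that either enrolled subject has such a condition. The counting language feeds no summary table, because only listings are produced. The low cost of the edit does not supply the missing benefit.

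**Conclusion.** No change is needed. As printed, no criterion in SAP 7.2.2 ties AST or ALT above 3 × ULN to bilirubin above 2 × ULN on the same date. The composite omits no record that the version with an AST or ALT term would include; it can only include more. The most that could differ is a label on an already listed record, for at most 2 subjects. No estimate, conclusion or management decision would change; dose modification follows protocol Table 5-3, which does not use this row.

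This rests on two conditions in the current documents: reporting stays at by-subject listings for the two enrolled subjects, and those listings show AST, ALT, ALP and bilirubin by date. If these liver criteria were reused for a larger study with summary counts, the purpose of the composite would need to be stated.
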